### 4.3 Key Definitions

The following definitions will be used:

- Date of the First Study Treatment Administration: The date of the first study treatment administration is defined as the earliest date on which a study treatment was administered.
- Baseline: The Baseline value is defined as the last available valid, non-missing observation for each Participant prior to first study treatment administration on Day 1. Repeat and unscheduled assessments will be included in the derivation of the Baseline values only if Baseline value is missing.
- Change from Baseline: The change from Baseline value is defined as the difference between the result collected/derived at a particular visit and the Baseline value.

The change from Baseline value at each visit will be calculated for all continuous parameters using the following formula:

Change from Baseline Value = Result at specified visit – Baseline Value

The change from Baseline value will only be calculated if the specific visit result and the Baseline value for the parameter are both available and will be treated as missing otherwise.

• Study Day: The study day of an event is defined as the relative day of the event starting with the date of the first study treatment administration (reference date) as Day 1 (there will be no Day 0).

The study day of events occurring before the first study treatment administration will be calculated as:

```
Study Day = (Date of Event - Date of First Study Treatment Administration)
```

For events occurring on or after Day 1, study day will be calculated as:

CONFIDENTIAL
--------------

Study Day = (Date of Event - Date of First Study Treatment Administration) + 1

Study days will only be calculated for events with complete dates and will be undefined for events that are 'Ongoing' at the end of the study.

• Actual Time from First Dose (hours) in PK related outputs is defined as:

(Date/Time of PK Sample collection) – (Date/Start Time of First Dose on Day 1).

• Actual Time Deviation (hours) in PK related outputs is defined as:

(Actual PK Sample Collection Time Post Dose) – (Scheduled PK Sample Collection Time Post Dose).

• AE Duration: Adverse event duration (in days, to two decimal places), calculated as

(Resolution Date + Resolution Time) – (Onset Date + Onset Time)

AE duration will only be calculated for events with complete dates/times and will be undefined for events that are 'Ongoing' at the end of the study.

## 4.4 Multiple Comparisons and Multiplicity

No multiplicity adjustment will be carried out for this study.

### 4.5 Handling of Missing Data

In general, all data will be analysed as collected and missing values will not be imputed or replaced unless stated otherwise.

#### 4.6 Treatment Group and Visit Display Conventions

#### **Summary Table:**

In summary table, the representation as below:

- Arm A: 3 mg/kg MB05
- Arm B: 3 mg/kg EU-Synagis®
- Arm C: 3 mg/kg US-Synagis®
- Overall

#### **Data Listing:**

In data listing, the following labels will be used:

- Arm A: 3 mg/kg MB05
- Arm B: 3 mg/kg EU-Synagis®
- Arm C: 3 mg/kg US-Synagis®

#### Visit labels:

The following visit labels will be used:

- Screening (Listing only)
- Day -1 (Listing only)
- Baseline (Table only)
- Day 1

CONFIDENTIAL

- Day 2
- Day 3
- Day 4
- Day 5
- Day 6
- Day 8
- Day 15
- Day 22
- Day 29
- Day 36
- Day 43
- Day 57
- Day 71
- Day 85
- End of Study
- Early Termination (Listing only)
- Unscheduled (Listing only)

For listings, these labels will be used, with visit representing baseline (either screening/baseline or unscheduled visit marked as "[1]" with a footnote indicating it is baseline value). These visit displays will be sorted by date of visit within each Participant:

## **5** ANALYSIS POPULATIONS

### 5.1 Safety Analysis Set (SS)

The Safety Analysis Set will be defined as all randomized participants who received any amount of study treatment and will be based on the actual treatment received, if this differs from that to which the participant was randomized to. The Safety Analysis Set will be used for the summaries of all safety, baseline, and demographic data.

### 5.2 Pharmacokinetic Analysis Set (PKS)

The Pharmacokinetic Analysis Set will be defined as all randomized participants who received any amount of study treatment and where there is sufficient data for reliable estimates of  $C_{max}$  (as determined by the study Pharmacokineticist).

### 5.3 Per Protocol Pharmacokinetic Analysis Set

The per protocol pharmacokinetic analysis set will include all subjects in the PK Analysis Set who have no major protocol violations that impact on pharmacokinetics. Subjects who do not complete the sampling per schedule but have sufficient data points to construct each concentration-time profile will be considered PK evaluable.

### 5.4 Immunogenicity Analysis Set (IAS)

The Immunogenicity Analysis Set will be defined as all randomized participants who receive any amount of study treatment and who have at least 1 evaluable immunogenicity parameter post-dose and will be summarized according to the treatment actually received, if this differs from that to which the participant was randomized. The immunogenicity Analysis Set will be used for the summaries of all immunogenicity data.

## **6 PARTICIPANT DISPOSITION**

The following participant disposition information will be reported:

Summary of Disposition:

- Number of Participants Completed
- Number of Participants Not Completed
- Reason for Non-Completion (percentage denominator based on number of withdrawn Participants)

Counts and percentages will be reported for summary of disposition and will be provided using the Safety Analysis Set for treatment groups defined in Section 4.6.

Listings will be provided for summary of disposition along with the date of study completion/discontinuation and the primary reason for non-completion. The listing will be provided by treatment groups (Section 4.6) sorted by Participant Identification (ID) for the Safety Analysis Set.

## 7 ANALYSIS SET

The following analysis set information will be reported:

- Participants included in Safety Analysis Set
- Participants included in Pharmacokinetic Analysis Set
- Participants included in Per Protocol Pharmacokinetic Analysis Set
- Participants included in Immunogenicity Analysis Set

Counts and percentages for these participants under different population sets will be provided using the Safety Analysis Set for treatment groups defined in Section 4.6.

Listings will be provided by treatment groups (Section 4.6) sorted by Participant ID for the Safety Analysis Set.

### 8 PROTOCOL DEVIATIONS

The following protocol deviations, but not be limited will be reported:

- Inclusion/Exclusion Criteria participant enrolled without meeting eligibility criteria.
- Laboratory deviations in lab sample processing, storage or shipment, or lab kits/supplies.
- Visit Schedule visit window deviations, missed study visits.
- IP Dosing and/or Accountability participant received wrong treatment dosed outside of the protocol timepoints or received treatment not stored per protocol.
- Concomitant Medication participant received medication prohibited by the protocol.
- Study Procedure/Tests assessment window deviations, missed study assessments, incorrect order of assessments, assessments not conducted per protocol.
- Randomisation
- Safety Reporting (AEs/SAEs) SAEs not reported within the expected turn-aroundtime per regulatory reporting requirements (i.e., 24 hours from awareness). Pregnancy not reported within the expected turn-around time per regulatory reporting requirements (i.e., 24 hours from awareness).
- Protocol Discontinuation Criteria participant remained on the study after meeting protocol withdrawal criteria.
- Informed Consent any informed consent issues, including Participant not consented prior to study assessments/procedures commencing, new clinical study procedures performed before participant was re-consented, initial consent not signed/dated/ initialled per local regulatory guidelines.
- Data Protection and Privacy
- Participant Compliance compliance issues with study requirements including diet and physical activity restrictions, study visit attendance.

All protocol deviations will be assessed between Avance and the Sponsor during study before database lock and unblinding.

The number of participants with at least one protocol deviations, and the category of protocol deviations will be summarized in accordance with Section 4.2 using the Safety Analysis Set for treatment groups defined in Section 4.6.

Listing of all protocol deviations will be provided by treatment group (Section 4.6) sorted by Participant ID for the Safety Set A separate protocol deviation listing will be created for the Pharmacokinetic Analysis Set.

In addition, all available data collected in General Common Forms originating from the electronic Case Report Forms (eCRFs) will be provided in data listing by treatment groups (defined in Section 4.6) sorted by Participant ID for the Safety Set.

#### 9 DEMOGRAPHICS AND BASELINE INFORMATION

The demographics variables to be reported are listed below:

- Age (years) at baseline
- Sex
- Women of child-bearing potential
- Race
- Ethnicity
- Height (cm) at baseline
- Weight (kg) at baseline
- BMI (kg/m^2) at baseline

These variables will be summarized using descriptive statistics in accordance with Section 4.2 under the Safety Analysis Set for treatment groups defined in Section 4.6. Demographics variables will also be listed by treatment groups (Section 4.6) under the Safety analysis Set sorted by Participant ID.

The following baseline information analysis will be listed by treatment groups (Section 4.6) under the Safety analysis Set sorted by Participant ID.

- Urine Drug Screen
- Alcohol Breath Test
- Serology
- COVID-19 Test

## **10 MEDICAL HISTORY**

Medical history conditions will be coded using the version 25.0 of the Medical Dictionary for Regulatory Activities (MedDRA) that is available at the time of study commencement. Terms will be coded to the full MedDRA hierarchy, but the system organ class (SOC) and preferred terms (PT) will be of primary interest for the analysis. Where SOC and PT are reported, the display will be sorted by the descending order by SOC and then by PT in the Overall treatment group.

Medical history listings will be provided by treatment groups (Section 4.6) sorted by Participant ID for the Safety Analysis Set, along with start date, end date/ongoing status of medical history.

#### **11 PRIOR AND CONCOMITANT MEDICATION**

Prior and concomitant medications will be coded using World Health Organization Drug Dictionary (WHO-DD) (the version of WHODRUG GLOBAL B3 March 2022).

- Prior Medications: Prior medications are defined as any medication where the use was stopped prior to the first administration of the study medication.
- Concomitant Medications: Concomitant medications are defined as medications (other than the study drug) taken at least once after the start of first study drug administration.

Medications stopped prior to the day of first study drug administration will not be considered concomitant medications, but they will be coded by WHO-DD and listed. If a clear determination cannot be made as to whether the medication is concomitant or not due to missing or incomplete data, the medication will be treated as concomitant medication taken during the study.

The number and percentage of Participants using at least one concomitant medication will be displayed together with the number and percentage of Participants using at least one medication within each anatomical therapeutic class (ATC-Level 2) and preferred name. These will be summarized under the Safety Analysis Set for treatment groups defined in Section 4.6. Where ATC-Level 2 and preferred name are reported, the display will be sorted by the descending order by ATC-Level 2 and then by PT in the Overall treatment group.

Listing of full details of prior and concomitant medications (medication taken, therapeutic class, start and stop dates/ongoing status, indication, routes, frequency, and dosage) will be provided by treatment group (Section 4.6) sorted by Participant ID and start date for the Safety Analysis Set.

### **12 TREATMENT AND EXPOSURE**

All study drug administration information (study drug administered [Yes/No], reason not administered, date and time (start time/end time) of administration, location, route, total dose [mg]/total volume [mL], dose interruption, reason for dose interruption, start time of interruption, volume administered prior to interruption, dose restarted, following the protocol, reason for not following the protocol, and entire volume not administered ) will be listed by treatment group (Section 4.6) sorted by Participant ID and visit for the Safety Analysis Set.

Protocol Number: MB05-A-01-21 Document Status: Final 2.0 Version date: 15-Jun-2023

## **13 EFFICACY**

No efficacy analysis is planned for this study.

## **14 SAFETY**

All safety endpoints will be analyzed using the safety analysis set.

### 14.1 Adverse Events

AE verbatim terms will be coded using the version 25.0 of the Medical Dictionary for Regulatory Activities (MedDRA). AEs and SAEs are defined in the study protocol.

- Treatment Emergent Adverse Events (TEAEs) are defined as adverse events that occurred or worsened from the first administration of study drug. If determination cannot be made as to whether the event is treatment emergent due to missing or incomplete data, the adverse event will be treated as treatment emergent.
- Treatment-Related are defined as any TEAEs reported with the causality of "Possibly", "Probably", "Definitely" to study treatment.

All AE summaries will be restricted to TEAEs only.

The TEAE summaries will include:

- Overall Summary of TEAEs
  - o TEAEs
  - Treatment Related TEAEs
  - Serious TEAEs
  - Serious Treatment Related TEAEs
  - TEAEs leading to death
  - TEAEs leading to study withdrawal

The following table summaries will be presented by SOC and PT by treatment groups defined in Section 4.6:

- TEAE summary by SOC and PT
- TEAE summary by SOC, PT and Severity
- TEAE summary by SOC, PT and relationship (study treatment)
- Serious TEAE summary by SOC and PT
- Treatment Related TEAE summary by SOC and PT
- Serious Treatment-Related TEAE summary by SOC and PT
- Treatment Related TEAE summary by SOC, PT and Severity
- TEAE summary if events leading to study withdrawal by SOC and PT

The above items will be presented using summary tables, which will include the number of participants (%) experiencing an event and the number of events and the number of events. If a Participant experienced the same adverse event multiple times, this will only be counted once for the purpose of counting the number of Participants experiencing that adverse event. Summary tables will be done for the Safety Analysis Set for treatment groups defined in Section 4.6. Where SOC and PT are reported, the display will be sorted by the descending order by SOC and then by PT in the Overall treatment group.

All AEs will be listed and will include the verbatim term, SOC, PT, SAE, start/end date/time, causality/severity, relationship to study treatment, relationship to procedure of injection, outcome, action taken, and study withdrawal. A separate listing will be created for SAEs. These listings will be presented by treatment groups (Section 4.6) sorted by Participant ID and AE start date for the Safety Analysis Set, along with age, sex, race, and baseline weight of the Participant.

### 14.2 Safety Laboratory Assessments

The following laboratory measurements will be taken at the time points specified in the study procedure schedule (Section 20):

- Haematology: Haemoglobin, Haematocrit, Thrombocyte count (platelets), Reticulocyte count, White blood cells (WBC) count with differential: Neutrophil count, Eosinophil count, Basophil count, Lymphocyte count, and Monocyte count
- Coagulation: Prothrombin time (PT), International normalized ratio (INR), Activated partial thromboplastin time (aPTT) and Thrombin time (TT)/thrombin clotting time (TCT).
- Chemistry: Sodium, Potassium, Chloride, Bicarbonate, Phosphate, Calcium, Glucose, Amylase, Lipase, Uric acid, Albumin, Protein, Lactate dehydrogenase (LDH), Creatine kinase, Creatinine or creatinine clearance (Cockroft/Gault), Urea, Alkaline phosphatase (ALP), Alanine aminotransferase (ALT), Aspartate aminotransferase (AST), Gamma Glutamyl Transferase (GGT), Total bilirubin (total and direct), Total cholesterol, highdensity lipoprotein (HDL), low-density lipoprotein (LDL), Triglycerides, Magnesium
- Urinalysis and Urine Microscopy: pH, Specific gravity, Glucose, Protein, Ketones, Bilirubin, Blood, Nitrite, Urobilinogen, Leukocyte esterase

For the haematology, coagulation, chemistry, continuous data summary statistics (as described in Section 4.2) will be presented for values and change from baseline value at each scheduled post baseline visit.

In addition, Shift tables from Baseline at each visit for haematology, coagulation, and chemistry lab parameters (low, normal, and high) will also be presented using counts and percentages.

For urinalysis, the urinalysis table will present counts and percentages of normal, abnormal clinically significant and non-clinically significant for the reported results at baseline and each post baseline visit for all parameters (as described in Section 4.2)

These summary tables will be based on the Safety Analysis Set for treatment groups defined in Section 4.6.

The listings of laboratory parameters (haematology, coagulation, chemistry, and urinalysis) will include all the information collected. In addition, the observations that are used as the baseline record (value) for each parameter will be flagged, and the change from baseline values (where applicable) at each scheduled post baseline (scheduled and unscheduled) visit will be presented. A separate listing for individual subject profiles to include any laboratory parameters with at least one post-dose value outside the laboratory's reference ranges will be presented. These listings will be presented by treatment groups (Section 4.6) sorted by Participant ID and visit for the Safety Analysis Set, along with age, sex, race, and baseline weight of the Participant.

## 14.3 Vital Sign Assessments

The following vital signs measurements will be taken at the time points specified in the study procedure schedule (section 20):

- Systolic blood pressure (SBP) (mmHg)
- Diastolic blood pressure (DBP) (mmHg)
- Pulse Rate (beats/min)
- Respiratory rate (breaths/min)
- Body Temperature (°C)
- Overall Clinical Interpretation:
  - o Normal
  - Abnormal NCS (Not Clinically Significant)
  - Abnormal CS (Clinically Significant)

The parameter names that will be used in the outputs will comprise of the test name and the unit of measure, for example, 'Systolic Blood Pressure (mmHg)'. Parameters will be sorted in the order that the measurements were collected in on the Vital Signs eCRF page within the tables and listings.

Summary statistics for vital sign parameters in accordance to Section 4.2 will be presented for baseline and for each scheduled post-baseline visit (which also includes change from baseline). In addition, overall clinical interpretation result (Normal, Abnormal not clinically significant, Abnormal and clinically significant,) will be summarized by counts and percentages for baseline and for each scheduled post baseline visit. These summary tables will be done for the Safety Analysis Set for treatment groups defined in Section 4.6.

The listing of vital sign parameters will include all the information collected. In addition, the observations that are used as the baseline record (value) for each parameter will be flagged, and the change from baseline values at each post baseline (scheduled and unscheduled) visit will be presented. This listing will be presented by treatment groups (Section 4.6) sorted by Participant ID and visit for the Safety Analysis Set, along with age, sex, race, and baseline weight of the Participant.

## 14.4 12-Lead Electrocardiogram (ECG)

The following ECG measurements will be taken at the time points specified in the study procedure schedule (Section 20):

- Heart Rate (bpm)
- QT interval (msec)

CONFIDENTIAL

- PR interval (msec)
- QRS duration (msec)
- QTcF (msec)
- Overall ECG clinical interpretation
  - o Normal
  - Abnormal NCS (Not Clinically Significant)
  - Abnormal CS (Clinically Significant)

The parameter names that will be used in the outputs will comprise of the test name and the unit of measure, for example, 'Heart Rate (beats/min)'. Parameters will be sorted in the order that the measurements were collected in on the ECG eCRF page within the tables and listings.

For ECG triplicates, the mean of ECG triplicated, and the worst clinical interpretation will be taken as the ECG values for each participant at applicable visit.

Summary statistics for ECG parameters in accordance with Section 4.2 will be presented for baseline and for each scheduled post baseline visit (which also includes the change from baseline). In addition, overall ECG clinical interpretation result (Normal, Abnormal not clinically significant, and Abnormal clinically significant) will be summarized by counts and percentages for baseline and for each scheduled post baseline visit. These summary tables will be done for the Safety Analysis Set for treatment groups defined in Section 4.6.

The listing of ECG parameters will include all the information collected. In addition, the observations that are used as the baseline record (value) for each parameter will be flagged, and the change from baseline values at each post baseline (scheduled and unscheduled) visit will be presented. This listing will be presented by treatment group (Section 4.6) sorted by Participant ID and visit for the Safety Analysis Set, along with age, sex, race, and baseline weight of the Participant.

## 14.5 Physical Examinations

The listing of physical examinations (including full and symptom directed examinations) will include all the information collected. This listing will be presented by treatment group defined in Section 4.6, sorted by Participant ID and visit for the Safety Analysis Set.

#### 14.6 Pregnancy Test and Follicle Stimulating Hormone Test

The listing of pregnancy test (urine and serum based) and FSH test (post-menopausal females only) will include all the information collected. This listing will be presented by treatment group defined in Section 4.6, sorted by Participant ID and visit for the Safety Analysis Set.

#### 14.7 Injection Site Reaction

The following Injection Site Reaction measurements will be taken at the time points specified in the study procedure schedule (Section 20):

- Pain
- Tenderness
- Erythema/Redness
- Induration/Swelling

CONFIDENTIAL

Parameters will be sorted in the order that the measurements were collected in on the Injection Site Reaction eCRF page within the tables and listings.

The severity of the injection site reaction parameters will be summarized by counts and percentage for baseline and for each scheduled post-baseline visits. These summary tables will be done for the Safety Analysis Set for treatment groups defined in Section 4.6.

The listing of injection site reaction parameters will include all the information collected. In addition, the observations that are used as the baseline record for each parameter will be flagged, and date/time of assessment, location, and other reaction at injection site (Yes/No) will be presented. This listing will be presented by treatment groups (Section 4.6) sorted by Participant ID and visit for the Safety Analysis Set.

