#### 12.1.1 Injection Site Reaction Assessments

Injection site reactions may include:

- Pain
- Tenderness
- Erythema/redness
- Swelling/ induration
- Other (e.g., haemorrhage, haematoma and pruritus)

Injection site reactions will be graded as per the FDA Guidance for Industry document entitled *Toxicity Grading Scale for Healthy Adult and Adolescent Volunteers Enrolled in Preventive Vaccine Clinical Trials* (2007) as presented in Table 4.

Local Reaction to Injectable Product	Mild (Grade 1)	Moderate (Grade 2)	Severe (Grade 3)	Potentially Life- Threatening (Grade 4)
Pain	Does not interfere with activity	Repeated use of nonnarcotic pain reliever > 24 hours or interferes with activity	Any use of narcotic pain reliever or prevents daily activity	Emergency room (ER) visit or hospitalisation
Tenderness	Mild discomfort to touch	Discomfort with movement	Significant discomfort at rest	ER visit or hospitalisation
Erythema/Redness*	2.5 – 5 cm	5.1 – 10 cm	> 10 cm	Necrosis or exfoliative dermatitis
Induration/Swelling**	2.5-5 cm and does not interfere with activity		> 10 cm or prevents daily activity	Necrosis

\* In addition to grading the measured local reaction at the greatest single diameter, the measurement should be recorded as a continuous variable.

\*\* Induration/Swelling should be evaluated and graded using the functional scale as well as the actual measurement.

Injection site reaction types not meeting the above definitions (e.g., haemorrhage, haematoma, pruritis), will be graded according to the National Cancer Institute Common Terminology Criteria for AEs (NCI-CTCAE, Version 5.0) 5-point scale, as described in Section 12.2.1

below.

All injection site reactions will also be recorded as AEs, with the overall severity of the injection site reaction graded according to NCI-CTCAE criteria, Version 5.0.

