## 13.5.6 Injection Site Reactions

All individual injection site results will be presented in data listings. Frequency of severity will be summarised by reaction type (pain, tenderness, erythema/redness and swelling/induration, or other), assessment timepoint and treatment.

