# **18 CHANGES TO THE PLANNED ANALYSIS**

Not applicable.

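### SAP 14.7 leaves the 'other' injection-site reactions out of the severity tables that protocol 13.5.6 requires, and section 18 does not declare it

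*SAP*

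**What the plan says.** **Protocol.** Section 12.1.1 lists four named reaction types and a fifth, given as "Other (e.g., haemorrhage, haematoma and pruritus". It also sets the scale for the fifth: "Injection site reaction types not meeting the above definitions (e.g., haemorrhage, haematoma, pruritis), will be graded according to the National Cancer Institute" Common Terminology Criteria, version 5.0. Section 13.5.6 then specifies the analysis: "Frequency of severity will be summarised by reaction type (pain, tenderness, erythema/redness and swelling/induration, or other), assessment timepoint and treatment". Section 12.1.1 and the Appendix 1 notes also require every injection-site reaction to be recorded as an adverse event.

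**SAP.** Section 14.7 opens with "The following Injection Site Reaction measurements will be taken at the time points specified in the study procedure schedule (Section 20" and follows it with four bullets: pain, tenderness, redness and swelling. The planned table is then "The severity of the injection site reaction parameters will be summarized by counts and percentage for baseline and for each scheduled post-baseline visits". The fifth type appears only in the listing paragraph, where "date/time of assessment, location, and other reaction at injection site (Yes/No) will be presented". SAP section 1 says that differences from the protocol's statistical section will be detailed in section 18. Section 18 reads "Not applicable".

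**The concern.** The secondary safety endpoint in SAP 2.2.2 is the incidence, type and severity of injection-site reactions, with no restriction on type. A programmer who follows SAP 14.7 as written will produce severity tables for four types. A participant whose only local reaction is a haematoma or itching will contribute no reaction to any of those tables. Because section 18 is empty, a reader of the study report would not be told that a summary specified in the protocol had been left out.

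Local tolerability is a direct between-arm comparison in this trial, and haemorrhage, haematoma and pruritus are effects that the protocol chose to assess and grade after an intramuscular injection. The SAP gives no reason for treating them differently from the other four types.

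**Working it through.** No formula applies. The check is a comparison of texts.

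**Step 1. Required against planned**

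| Item | Protocol 12.1.1 and 13.5.6 | SAP 14.7 |
|---|---|---|
| Pain | severity table | severity table |
| Tenderness | severity table | severity table |
| Redness | severity table | severity table |
| Swelling | severity table | severity table |
| Other | severity table, graded on CTCAE v5.0 | listing only |
| Types tabulated | 5 | 4 |

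The shortfall is 5 − 4 = 1 type.

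**Step 2. Is the omission declared?** No. Section 18 is the place that SAP section 1 names for differences, and it is empty. The SAP's Summary of Changes for version 2.0 does not mention injection-site reactions either.

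**Step 3. Is there a severity to tabulate?** By protocol, yes, because 12.1.1 assigns a five-point scale to the fifth type. Whether the eCRF holds that grade at each timepoint cannot be confirmed. The Yes/No item in the SAP listing suggests that the detail may sit in the adverse event record instead.

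**Step 4. Does the adverse event route close the gap?** SAP 14.1 tabulates TEAEs by system organ class, preferred term and severity for each arm, with numbers of participants and events. A haematoma at the injection site should appear there. Three features limit this route:

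- *No timepoint.* Appendix 1 schedules seven post-dose assessments: 30 and 60 minutes on Day 1, then Days 2 to 6 (2 + 5 = 7). The TEAE tables have no breakdown by assessment.
- *Overall grade.* Protocol 12.1.1 gives the adverse event the overall severity of the reaction. Section 12.2.1 says that an event with several aspects takes its highest grade, and section 12.4 asks for a single diagnosis where signs share a cause.
- *No grouping.* SAP 14.1 plans no table that collects the injection-site events, so they may be spread over several preferred terms.

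An illustration of the second feature, using an assumed case: a participant has moderate pain and a mild haematoma, and the site records one injection-site reaction as the adverse event. The event carries the higher grade. SAP 14.7 shows the pain. The type and grade of the haematoma appear separately in neither table.

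**The case against.** The strongest reply is that nothing is lost from the endpoint. Every injection-site reaction is also an adverse event, so its incidence, type and severity by arm are summarised under SAP 14.1. For the 'other' type the scale is CTCAE in both places, so there is no clash of scales. The SAP 14.7 listing includes all the information collected, and the Yes/No flag is an addition to it. The endpoint is descriptive, with no hypothesis test.

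Most of this stands, and it rules out several stronger readings that a reader might infer:

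- *That the endpoint is understated.* The documents do not support this, because the events reach the TEAE tables by arm.
- *That each participant with only an 'other' reaction lowers the arm's reaction rate by 1/47 = 2.1 percentage points.* Neither document plans an any-reaction rate in the injection-site tables, so there is no rate to lower. A participant with only a haematoma is correctly shown as having none of the four tabulated signs.
- *That SAP 14.7 collapses the 30- and 60-minute readings on Day 1 into one visit.* Its opening sentence refers to the scheduled time points, and SAP 4.2 presents scheduled visits or time points. Nothing says that the readings will be merged.
- *That the trehalose in MB05, absent from the comparators, makes a local difference likely.* Protocol 4.3 mentions trehalose only as not expected to affect PK. Neither document links it to local reactions.

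The reply does not remove the mismatch itself. Protocol 13.5.6 asks for "summarised by reaction type (pain, tenderness, erythema/redness and swelling/induration, or other), assessment timepoint and treatment", and the TEAE tables give neither the timepoint nor, for a composite reaction, the component.

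**Conclusion.** The point holds as a protocol–SAP inconsistency in a secondary safety summary. Following the SAP as written omits one of five reaction types from the severity tables that the protocol specifies, without declaring it. The TEAE tables compensate in part: by arm, but not by timepoint, and possibly only at the overall grade of the reaction.

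The effect on the results cannot be sized, because no expected frequency of 'other' reactions is given. The primary bioequivalence analysis is not touched.

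The conclusion assumes that the parameters tabulated in SAP 14.7 are the four bulleted there, which is the plain reading. How much the TEAE tables miss for composite reactions depends on how sites split or combine local signs when they record adverse events.

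**What to change.** In SAP 14.7, add 'Other (specified), NCI-CTCAE v5.0 grade' to the parameters summarised, and tabulate it by assessment timepoint and arm as protocol 13.5.6 requires. It would help to state that the 30- and 60-minute assessments on Day 1 are shown separately.

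If the eCRF holds only a Yes/No flag at each timepoint, take the type and grade from the linked adverse event record, say so in section 18, and cross-refer to section 14.1.

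A row for participants with any reaction, and a worst-grade row by type, would be useful for the incidence part of the endpoint. They are optional, since protocol 13.5.6 does not ask for them.

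The cost is SAP wording and a few table rows, plus possible programming to link the injection-site and adverse event data.
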